- Aims 2 and 3 will test the feasibility of an 8-session web-based interpretation training program called "MindTrails" among individuals with moderate to severe anxiety symptoms (based on screening at the PIMH site). Participants will be randomly assigned to either active CBM-I (100% positive scenario training) or a 50% positive/50% negative condition, or a no scenario control condition. Half the participants in each of these 3 conditions will receive an anxious imagery prime prior to each training session, and half will receive a neutral imagery prime, resulting in a 3 training condition x 2 prime design. Feasibility will be determined by analyses of recruitment, attrition, acceptance of randomization, adherence to and appropriateness of the measurement model, caseness, extent of missing data, and safety. Additionally, target engagement (change in interpretation bias) and preliminary tests of effectiveness at reducing anxiety symptoms will be evaluated.
- Furthermore, a group of up to 10 participants will be randomly selected to receive the additional benefit of coaching. These participants will be contacted through email and directed to a separate consent form regarding the coaching protocol. The coaching protocol itself will involve a series of brief phone calls and/or Google Voice messaging sessions with the purpose of increasing adherence to the MindTrails program. The coaching contacts will involve discussing goals for login and site use, reinforcing use, and addressing questions about the site's functionality and applicability. This is not therapy by phone and participant disclosure of symptoms will not be required. We will use undergraduate and graduate student-level coaches and will follow an adapted version of the standard training protocol for TeleCoach (with consultation from [name], developer of the intervention). The coaching protocol has already been approved in UVA IRB SBS protocol 2017-0234-00. Including this additional service is expected to help refine the coaching protocol as well as increase adherence to the program.

- **Materials:**

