 - If individuals score above the established cutoff during their Project Implicit Mental Health study, they will be alerted to their eligibility for this study via a message added to their standard debriefing form following completion of the anxiety and depression study measures. (See attached Debriefing forms to see additions to the standard Project Implicit Mental Health form). Individuals may also see if they're eligible for the study by clicking an icon at the front page of the Project Implicit Mental Health site.
 - Following consent, participants who are eligible will be randomly assigned to one of 6 groups (active CBM-I + anxiety imagery prime, 50/50 + anxiety imagery prime, no scenario control + anxiety imagery prime, active CBM-I + neutral imagery prime, 50/50 + neutral imagery prime, no scenario control + neutral imagery prime condition), matched for gender ratio. Participants will be asked to complete eight sessions of their assigned intervention, over the course of four weeks (~two sessions per week). Each session will last approximately 20 minutes.
 - Prior to the first session, participants will receive a rationale about the intervention, followed by a series of questionnaires and online tasks assessing psychological symptoms, mental health history and demographics, interpretation bias, quality of life, etc. Following the third, sixth, and eighth sessions, participants will also be asked to complete the assessment battery. Finally, two months after the intervention, participants will be asked to complete a follow-up assessment, before being debriefed and provided with feedback about their change in symptom scores. Please see Measures Schedule in the Appendix for list of specific measures at each time point.
 - Following completion of the first training session, up to 10 participants will be randomly selected to receive coaching. These participants will be emailed upon their selection and directed to a separate consent form. After completion of the consent process, participants will participate in weekly sessions with their coaches. These sessions will be used to discuss usability and engagement issues with the MindTrails program and will be held either over the phone or through Google Voice messaging. Coaching will stop after the (eighth) MindTrails session. We will offer \$40 to participants for taking part in coaching.

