There is a possibility that the active CBM interventions will not work and the participants assigned to these conditions will not improve. Moreover, it is expected that participants assigned to the control conditions will not improve (though we do not expect symptom worsening beyond normal variations, and all participants will be offered an active CBM condition following the end of their 2-month follow-up assessment).

Notwithstanding, there is a possibility of worsening symptoms, which we will monitor. Across studies and conditions, participants may experience some anxiety or discomfort from the discussion of their personal information, completion of the symptom questionnaire, and the anxiety imagery. However, completion of these measures is a critical component of the research, and is not expected to cause enduring distress. Some participants may initially feel some discomfort discussing sensitive topics over the Internet, or over the phone for those participants receiving coaching, which is one reason we are not requesting last names. Finally, the lack of contact with a therapist was deemed important to appropriately test the feasibility of these interventions through an online platform, but we recognize that this limits our ability to individually tailor treatments, or respond to unique concerns that arise. This is one reason that we note how to contact the researchers (and the technical support staff) at numerous places at the website, and also make clear in multiple places at the site that MindTrails does not provide specific diagnostic or medical advice on our website, and we are limited in how we can respond to your responses.

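### Does coaching up to 10 randomised participants distort the attrition, completion and effectiveness results?

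*Combined protocol and SAP*

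**What the plan says.** The Study Overview describes a trial with six groups (three training conditions by two imagery primes) and eight web sessions. Its Procedure for Aims 2 and 3 adds: "Following completion of the first training session, up to 10 participants will be randomly selected to receive coaching". Those selected are emailed and sent to a separate consent form. After consent, "participants will participate in weekly sessions with their coaches", by phone or messaging, until the eighth programme session, and they are offered $40. The account of Aims 2 and 3 says coaching is given "with the purpose of increasing adherence to the MindTrails program", and later: "Including this additional service is expected to help refine the coaching protocol as well as increase adherence to the program".

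The same account defines the trial's targets. "Feasibility will be determined by analyses of recruitment, attrition, acceptance of randomization, adherence to and appropriateness of the measurement model", followed by caseness, missing data and safety. It adds that "target engagement (change in interpretation bias) and preliminary tests of effectiveness at reducing anxiety symptoms will be evaluated". Under Risks & Benefits, the safety monitor receives completion and attrition rates by masked condition. That section also says that "the lack of contact with a therapist was deemed important to appropriately test the feasibility of these interventions through an online platform".

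The text does not state whether those selected are kept, excluded or flagged in the analyses, or whether the draw is stratified by group. It refers to a separately approved coaching protocol and a separate coaching consent form. Neither is among the documents available here, and either might cover the point.

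**The concern.** A feasibility trial of self-guided web training gives some of its randomised participants regular live contact, with the stated aim of improving use of the programme. Attrition and missing data are feasibility criteria, so coaching acts directly on what the trial measures. Outcome batteries follow sessions 3, 6 and 8. Anyone coached through to session 8 is therefore more likely to supply outcome data and will be over-represented among completers. A simple random draw of ten can also fall unevenly over six groups. With no stated rule, keeping or dropping these people could be decided after the results are seen. At stake would be completion rates that overstate unassisted use, and group comparisons tilted by where the coached participants fell.

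**Working it through.** The documents contain no sample-size, dropout or coaching-effect figure to reproduce, so the check bounds the possible distortion.

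**Inputs from the documents.** Up to 10 selected; six groups; N = 1,000 planned and 1,710 ever enrolled (Participant Groups; the second figure may include about 100 MTurk pilot raters).

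**Assumptions.** Equal groups, so n = 1,000/6 = 167 or 1,710/6 = 285. Session-8 completion b = 10% to 20% without coaching and 80% with it. All ten accept.

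1. **Share coached.** 10/1,000 = 1.0%; 10/1,710 = 0.58%.

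2. **Shift in overall completion**, 10 × (0.80 − b)/N, against the standard error √(b(1 − b)/N):
   - N = 1,000: 7/1,000 = 0.7 points (SE 0.95) at b = 10%; 6/1,000 = 0.6 points (SE 1.26) at b = 20%.
   - N = 1,710: 7/1,710 = 0.41 points (SE 0.73); 6/1,710 = 0.35 points (SE 0.97).
   - The ceiling, where all ten would have dropped out but all complete, is 1.0 or 0.58 points.

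3. **Uneven draw.** With ten people spread at random over six equal groups, the chance that some group gets four or more is 0.40. The shift in that group is 4 × (0.80 − b)/n:
   - n = 167: 2.8/167 = 1.7 points (SE of the group's rate 2.3) and 2.4/167 = 1.4 points (SE 3.1). The SE of a difference between two groups is √2 times as large, 3.3 and 4.4.
   - n = 285: 2.8/285 = 1.0 point (SE 1.8) and 2.4/285 = 0.8 points (SE 2.4).

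4. **These shifts are overstated.** Only people who finished session 1 can be drawn, and their uncoached completion must exceed the rate among all randomised. If half finish session 1 (assumption), b among them is 20% to 40%. Step 3 at n = 285 then gives 4 × 0.60/285 = 0.84 down to 4 × 0.40/285 = 0.56 points.

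5. **Effectiveness, all randomised.** Suppose coaching adds 0.5 SD (assumption) and all ten fall in one training condition. The bias is 0.5 × 10/(N/3), against SE √(2/(N/3)) for a two-condition difference. N = 1,000 gives 0.015 SD against 0.077; N = 1,710 gives 0.009 SD against 0.059.

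6. **Completers only.** The coached share of completers is 8/(b(N − 10) + 8).
   - N = 1,000: 8/107 = 7.5% and 8/206 = 3.9%.
   - N = 1,710: 8/178 = 4.5% and 8/348 = 2.3%.
   - In a group of 167 with four coached: 3.2/(0.1 × 162.7 + 3.2) = 16.4%, or 9.0% at b = 20%. If coached completers differ from the rest by 0.5 SD, the first gives a bias of 0.164 × 0.5 = 0.08 SD. That group has about 19.5 completers and an uncoached group about 16.7, so the SE of their difference is √(1/19.5 + 1/16.7) = 0.33 SD.

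**The case for a change.** The strongest case for acting is that the trial's main purpose is feasibility, the plan itself expects coaching to raise adherence, and a pre-stated rule costs one sentence and one flag. Exposure also grows if completion is very low. At 5% completion with all ten finishing, the coached would be 10/50 = 20% of completers at N = 1,000, or 10/85.5 = 11.7% at N = 1,710. Live weekly contact sits awkwardly beside the reason given for testing without a therapist.

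The facts of the coaching stand, as does the silence on handling. Four parts do not carry the weight placed on them.

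- That those selected stay in their groups, or that the draw ignores group, is read into silence.
- The stated premise concerns therapist contact. The plan says coaching is not therapy and that coaches tell participants they are not therapists. This is a tension rather than a contradiction.
- In the feasibility list, adherence refers to the measurement model. The point has to rest on attrition, missing data and the reported completion rates.
- A share of completers is not a bias, because some coached participants would have finished anyway.

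Nor is excluding coached participants from the primary comparisons clearly better. Coaching needs separate consent, so those actually coached are self-selected, and dropping them is a post-randomisation exclusion. Drawing coached participants from a separate non-randomised group is no longer possible, because the Continuation section says data collection ended in January 2019.

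**Conclusion.** No change to the plan follows. The gap is an unstated handling rule for at most ten people. On the assumed rates it moves overall completion by about 0.4 to 0.7 points and makes the coached about 2% to 7% of session-8 completers. The bias in an all-randomised effectiveness comparison is at most 0.015 SD, even with a 0.5 SD coaching effect and all ten in one training condition. Each of these shifts is below one standard error. Only the ceiling of 1.0 point at N = 1,000 reaches about one standard error, and it requires every selected person to be turned from certain dropout into a completer.

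No systematic tilt between arms is expected, given random selection, equal allocation and similar session-1 completion. A competent analyst would keep all randomised participants in the main comparison, report how many were selected for coaching in each condition, and check completion rates and completer analyses without them. Requiring this in the plan would not be expected to alter any conclusion. The completion rates and the coaching effect are assumptions; if completion were near 5%, completer summaries would need the most care.

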Volunteers who take the DASS-anxiety, either to determine if they are eligible for this study, or as part of the anxiety study at Project Implicit Mental Health will be told whether they qualify for the experimental anxiety intervention. For those who are eligible, a link to more information about the intervention will appear (see sample text in Appendix at the "Invitation to Participate" and "About MindTrails" pages).

Individuals interested in the intervention that do not qualify for the study will see text (similar to the following) notifying them that they are ineligible:

"Thank you for completing our assessment.

Unfortunately, you do not currently qualify for the study, but we appreciate your interest. We want to be sure we are offering the program to people we think are most likely to find it helpful.

If you wish to participate in other research, we encourage you to visit the Project Implicit site, implicit.harvard.edu, where there are other studies that you can try today, or complete another study at Project Implicit Mental Health, implicitmentalhealth.com.

To access treatment for your anxiety, please see the following list of Mental Health Resources.

Thank you for your interest!

Note. You are welcome to complete the eligibility questionnaire at a later time to determine if your eligibility changes (e.g., based on symptom changes or new study criteria).

Do participants have any limitations on their ability to consent ? No

Describe the limitations on their ability to consent:

What are the consent processes for this study?

Participants will be provided an opportunity to read the consent form (different versions for the anxious pilot Ps, expert user group, and mTurk pilot Ps are attached for Aim 1, and see Appendix for Aim 2 consent). There will be a separate consent form for the participants selected to receive coaching. We will be clear that participants have the right to withdraw from the study at any time. Coaching participants will receive \$40 for participating in coaching.

Will participants be deceived and/or have information withheld from them about the study? Yes

Explain what is being withheld or describe the deception. Justify why the deception and/or the withholding of information from the participants is necessary.

Participants will not be told the full purpose of the study until debriefing. There will be no deception.

Will participants be debriefed? Yes

Describe your debriefing procedures:

Once data files are downloaded, they will be stored securely on an investigator's computer. Results will be reported in aggregate.

At the software level, our security model is built on the popular Spring Security Framework. We currently use a form based authentication (a web login form) that provides the following basic projections and features:

- Every URL in the site requires authentication.
- CSRF attack prevention (http://en.wikipedia.org/wiki/Cross-site_request_forgery)
- Session Fixation Protection (http://en.wikipedia.org/wiki/Session_fixation)
- Security header integration
- HTTP Strict Transport Security for secure requests
- X-Content-Type-Options integration
- Cache Control
- X-XSS-Protection integration
- X-Frame-Options integration to help prevent Clickjacking

How will data/materials be reported for this study? Will the results be reported in aggregate or will individual data be discussed?

Results will be reported in aggregate.

If a participant decides to withdraw from the study, how will you handle their data?

We do not delete any of the information we have previously collected on a participant when they withdraw from the study.

Do you plan to publish your raw data after the study is completed (i.e. open-access or open source publishing)? Yes

Will other parties (i.e. other corporations, institutions, researchers) have access to or retain a copy of the data? Yes

International Research

Risks & Benefits

You have indicated that this study will include the **2 items** displayed in the list below. These **2 items** are areas that often require more scrutiny from the Board. When framing your responses regarding the risks in this study, address the study as a whole, and also consider the **2 items** specifically as well.

Items:

1. includes students
2. deception

Is loss of confidentiality and/or privacy a risk to participants? No

Describe any remaining potential risks to participants. For example, are any of your participants or participant groups "risk sensitive"? Include information about the probability of harm (i.e. how likely it is that harm will occur). What will be done to reduce risk to participants? If something unexpected involving risk happens, how will you handle it?

There is a possibility that the active CBM interventions will not work and the participants assigned to these conditions will not improve. Moreover, it is expected that participants assigned to the control conditions will not improve (though we do not expect symptom worsening beyond normal variations, and all participants will be offered an active CBM condition following the end of their 2-month follow-up assessment).

Notwithstanding, there is a possibility of worsening symptoms, which we will monitor. Across studies and conditions, participants may experience some anxiety or discomfort from the discussion of their personal information, completion of the symptom questionnaire, and the anxiety imagery. However, completion of these measures is a critical component of the research, and is not expected to cause enduring distress. Some participants may initially feel some discomfort discussing sensitive topics over the Internet, or over the phone for those participants receiving coaching, which is one reason we are not requesting last names. Finally, the lack of contact with a therapist was deemed important to appropriately test the feasibility of these interventions through an online platform, but we recognize that this limits our ability to individually tailor treatments, or respond to unique concerns that arise. This is one reason that we note how to contact the researchers (and the technical support staff) at numerous places at the website, and also make clear in multiple places at the site that MindTrails does not provide specific diagnostic or medical advice on our website, and we are limited in how we can respond to your responses.

Participants will be clearly instructed that they have the right to withdraw from the study at any time without penalty. Further, we will have trained staff to manage emails submitted to the research team that are of a clinical nature (separate staff are in place to handle concerns related to technical difficulties). In particular, [name], the Principal Investigator and a licensed clinical psychologist, will be available to respond to any clinical issues. Coaches will also notify [name] regarding any clinical issues that participants may express during coaching sessions. We also provide extensive information at the MindTrails website about how and where to access treatment and mental health resources, and have these links included in the debriefing form to ensure participants are aware of the resources. Importantly though, we will also make clear at the site that we are not offering personal therapy or diagnostic advice, and will provide referrals for hotlines and other emergency contacts at the site should those be needed. Coaches will also make it clear to their participants that they are not therapists and cannot offer therapy or diagnosis and will direct participants to other resources if needed. If substantial worsening of a participant's anxiety symptoms occurs (regardless of training condition) during sessions 2 thru 8, as evidenced by more than a 50% increase in symptoms relative to that person's baseline score, he or she will be notified of the change and we will offer to help the participant find alternate treatment options. The 50% increase criterion was selected because a change of 50% matches the definition of a "reversal" of a treatment gain in the sudden gains literature (e.g., Tang & DeRubeis, 1999).

The intervention email address inbox will be checked daily for clinically-relevant messages from participants, and all clinical emails will be addressed within 24 hours. Though unexpected, given that no questions explicitly ask about suicidality, in the event that a participant indicates suicidal intent via email to researchers, we will: a) email the person information about how to access emergency services, national suicide hotlines, and suicide prevention websites, and b) offer the participant the opportunity to speak with [name] (or another on-call licensed clinician if [name] cannot be reached). Specifically, we will ask the participant to provide his or her phone number so that the licensed clinical psychologist can call the individual to more directly help connect the person with services, including both emergency hotlines and local therapy options. This protocol will also be followed if a participant indicates

suicidal intent during a coaching session. Note, this approach is similar to what we do in our lab, which has worked well for more than a dozen years. Given this possibility, we will clearly note the limits of confidentiality related to mandating reporting requirements in the informed consent document (i.e., if we learn of possible child abuse or neglect, or danger to self or others).

Further, all participants in the control conditions will be offered one of the active CBM interventions after they have completed the control training sessions and their 2-month follow-up assessment.

To help participants make informed choices about whether to pursue subsequent care, at the completion of the follow-up assessment participants will receive automated, individualized feedback about their performance, which will be written in an understandable and sensitive way. This will include a summary of their symptom scores, and how these have changed over time. They will also receive information (e.g., web site links) about how to identify and access alternate treatments, such as local providers, though we will be clear we are not endorsing any particular provider. Finally, as part of the debriefing process, participants will be given psychoeducation about cognitive biases and these biases' hypothesized role in symptom onset and recovery.

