- **Procedure for Aim 1:** Once the materials and training programs (termed the "MindTrails" Project) are fully assembled and ready for testing, we will solicit feedback from two groups: 1) a small test group of highly anxious participants (who will be compensated \$40 for their study visit, which will last approximately 2 hours); 2) an expert advisory board (who we do not plan to provide with financial compensation, given they will be participating as a professional courtesy). Both groups will try out the tasks and complete the measures to provide feedback on the programs' usability and acceptability via a survey and semi-structured interview (see above measures). We will assess numerous aspects of user experience, including clarity of the materials, ease of navigating the site, appropriateness of the intervention materials (re. language used, targets selected for stimuli), affective response to the materials, and extent materials are engaging and acceptable, perceived measurement burden of the assessment battery, etc. The semi-structured interview for each participant will follow completion of the user experience questionnaire, so that the interviewer can probe the responses and ask follow-up questions about potential ways to address the identified weaknesses of the program (e.g., participants' ideas about ways to make the tasks more engaging, the instructions clearer, etc.). These interviews will be conducted by the PI or trained project staff and graduate student collaborators on the project. This feedback will be used to modify all aspects of the programs in preparation for Aims 2 and 3.
- Note, we will also pilot the MindTrails site materials (e.g., CBM scenarios) on mobile phones using analogous procedures.

- **Procedure for Aims 2 and 3:** This study will be completed over the Internet, through an extension of Project Implicit Mental Health (www.implicitmentalhealth.com). Participants will be individuals recruited directly from the Project Implicit Mental Health website, as well as those who are invited to the site through a variety of online and offline advertisements and outreach efforts. The target population will be adults age 18 and over who score in the moderate to extremely severe anxiety range (i.e., 10 or higher) on the Depression, Anxiety, Stress Scales – Short Form: Anxiety Subscale (DASS21-AS).

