 - If participants are randomly assigned to a control condition, they will be offered the opportunity to complete one of the actual interventions following completion of the study.

Is this study topic relevant to cancer risk factors, prevention, cancer treatment, or survivorship (e.g., pain, financial toxicity etc.), or will the study purposefully include participants currently or previously diagnosed with cancer, or their caregivers (required)

(optional) **Study Overview file upload:** Below you have the option to upload additional files to help the Board better understand your study. You are not required to provide any additional explanation beyond completing the text boxes provided in this Study Overview section; however, for example, if you are using a new technology or a complicated process that would be more easily demonstrated with image or video, you can upload the file here.

Participant Groups

Participant Group Name: Anxious participants

Age Range (years): 18 and older

Vulnerable populations: includes students

Maximum number of participants, in this group, expected to enroll over the life of the study: 1800

Minimum number of participants, in this group, expected to enroll over the life of the study: (required)

Total number of participants, in this group, ever enrolled: 1710

Approximate number of participants, in this group, currently enrolled: 0

Future Enrollment: We are performing data analysis only, in this group (i.e. we are not actively collecting data from participants in this group)

Have participants, in this group, withdrawn from the study in the past year? No

Describe the participants in this group.

Gender: Mixed
Race: All/any
Estimated number of participants: 1000 (plus ~100 MTurk pilot participants)

The target populations for Aims 2 and 3 will be adults aged 18 and older who experience distress and/or impairment following from symptoms of anxiety. They will be selected based on established cut points on symptom screening measures. Specifically, the DASS21-AS will be used to determine eligibility. Individuals who score 10 or higher (suggesting moderate to extremely severe anxiety) on this measure at will be invited to participate in the study. Participants will be recruited via online recruitment methods (Craigslist, Project Implicit Mental Health, Facebook, etc.)

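### The individual worsening alert (more than 50% above own baseline) cannot fire for a participant whose baseline is at least two thirds of the alert measure's maximum, and the available text has no other score-based individual criterion

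*Combined protocol and SAP*

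**What the plan says.** Risks & Benefits (combined protocol and SAP) accepts that "there is a possibility of worsening symptoms, which we will monitor". The only individual rule in the available text that rests on a symptom score follows shortly after. It covers sessions 2 to 8, applies in every training condition, and defines substantial worsening "as evidenced by more than a 50% increase in symptoms relative to" the person's own baseline. When it is met, "he or she will be notified of the change and we will offer to help the participant find alternate treatment options". The 50% figure is justified by analogy with the definition of a reversal in the sudden-gains literature. The text does not discuss high baselines or a scale ceiling.

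Entry is open-ended at the top. Study Overview (Procedure for Aims 2 and 3) targets "adults age 18 and over who score in the moderate to extremely severe anxiety range", and Participant Groups repeats the cut: "Individuals who score 10 or higher (suggesting moderate to extremely severe anxiety) on this measure". That measure is the DASS21 anxiety subscale, used for screening.

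The rule does not name the measure it is applied to. For the instruments at each time point the Study Overview says "Please see Measures Schedule in the Appendix for list of specific measures at each time point". Neither that appendix nor the approved measures file listed under Data Sources Upload is in the text available for review.

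**The concern.** The training is delivered without a therapist, and half of each training condition receives an anxious imagery prime. A score-based alert is therefore the one route by which the study team would approach a worsening participant unprompted during training. A purely proportional rule on a bounded scale stops working at the top: above a certain baseline, no attainable score satisfies it. Someone who starts high and becomes clearly worse would get neither the notification nor the offer of help.

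There is also a reporting consequence. Study Overview lists safety among the feasibility analyses. No worsening rate by this rule is planned in the text. If one were reported, every participant above that baseline would count as not worsened by construction.

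**Working it through.** The plan states no figure to reproduce here, only the threshold. The check is algebra, and it needs no unstated scale maximum.

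**Inputs**
- Alert condition (Risks & Benefits): follow-up score s > 1.5b, where b is the participant's own baseline. The inequality is strict because the rule says more than 50%.
- Scale: maximum M, higher is worse. M is not given, so it stays a symbol.
- Entry cut (Study Overview, Participant Groups): 10 or higher on the screening measure, no upper limit.

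**Step 1: when can the alert fire?** It needs s > 1.5b and s ≤ M together. Such a score can exist only if 1.5b < M, that is b < 2M/3. At b = 2M/3 the score would have to be strictly above M, so the boundary itself is excluded.

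**Step 2: behaviour below the limit.** Write f = b/M. The rise must exceed f/2 as a share of M, and 0.5f/(1 − f) as a share of the room left, M − b.

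| Baseline, share of M | Rise must exceed, share of M | Rise must exceed, share of room left |
|---|---|---|
| 25% | 12.5% | 16.7% |
| 40% | 20.0% | 33.3% |
| 50% | 25.0% | 50.0% |
| 60% | 30.0% | 75.0% |
| 66.7% or above | unattainable | unattainable |

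**Step 3: is the gap only a lack of room to worsen?** No. At f = 0.70 the alert needs a score above 1.5 × 0.70M = 1.05M, which does not exist. Yet the participant can still rise by M − 0.70M = 0.30M. A participant at f = 0.25 is notified after a rise just over 0.125M. So a rise more than twice as large can go unflagged.

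**Step 4: illustrative cut scores (maxima assumed, not in the documents).** The limit 2M/3 is 14 for M = 21 and 28 for M = 42. With M = 42, a baseline of 26 needs a score above 39, which is attainable; a baseline of 28 needs a score above 42, which is not. If the alert used the screening measure with its entry cut of 10, the share of the eligible score range in which it cannot fire would be (M − 2M/3)/(M − 10):
- M = 30: 10/20 = 50%
- M = 36: 12/26 = 46%
- M = 42: 14/32 = 44%
- M = 48: 16/38 = 42%
- M = 60: 20/50 = 40%

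These are shares of a score range, not of participants.

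**Step 5: does another safeguard do the same job?**
- Site resources: "We also provide extensive information at the MindTrails website about how and where to access treatment and mental health resources". These are open to all, but the participant must look for them.
- Inbox checked daily, and the suicidal-intent procedure: both depend on the participant disclosing something.
- Coaches: up to 10 participants. Against 1710 ever enrolled in the group, 10/1710 = 0.6%. That group's description also covers about 100 online pilot raters; without them it is 10/1610, still 0.6%.
- Weekly investigator meetings: adverse events and participant safety are discussed, but no individual score check is described.
- Independent safety monitor: reviews the protocol and safety provisions before launch, then every 6 months receives summaries by masked condition and a de-identified data set. No individual score threshold is stated. The programme itself is short: "Participants will be asked to complete eight sessions of their assigned intervention, over the course of four weeks".
- Individual score feedback: given on completing the 2-month follow-up, so after training.

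**The case against.** The strongest reply has four parts.

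First, a reader might infer that the most severe entrants are the ones the alert cannot reach. The documents do not support that. The extremely severe label belongs to the screening measure, and the alert measure is unnamed. The assessment battery is given before session 1 and after sessions 3, 6 and 8, whereas the alert covers sessions 2 to 8, so it may run on a different instrument or schedule. A high screening score does not show a baseline of 2M/3 on the alert measure. This stands, and the point is limited to participants, if any, at or above 2M/3 on whatever measure the alert uses.

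Second, the missing appendix and measures file could hold the measure, its scoring or further alert detail. This also stands: the absence of a second criterion is a statement about the available text.

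Third, a reader might infer that worsening is otherwise unmonitored, or that needing a larger absolute rise at a higher baseline is itself an error. Neither follows. The safeguards in Step 5 are real, and the larger rise is inherent in any percentage rule. The defect is only that the rule becomes unattainable.

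Fourth, the plan gives a reason for 50%, classes the trial as low risk, and has closed data collection. These lower the priority. They do not answer the algebra, because the stated reason does not deal with a ceiling.

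**Conclusion.** The point holds as a minor design flaw in a safety rule. For any bounded measure on which higher is worse, the alert is unattainable from a baseline of 2M/3 upwards, and no other score-based individual criterion appears in the available text. Because entry has no upper limit and includes the extremely severe range, such participants can be enrolled.

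The two-thirds limit rests only on the wording of the rule and on the scale being bounded. Any specific cut score rests on an assumed measure and range. The number of participants affected cannot be computed, since no baseline distribution is given. Nothing in the documents shows that anyone was harmed or that a worsening participant was missed.

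**What to change.** **Future use of the rule.** Keep the 50% limb and add a second: notify if the score is more than 50% above baseline, or at least X points above baseline, with X fixed in advance by the study clinicians. The second limb can fire when b + X ≤ M, so it extends coverage to baselines of 2M/3 and above only if X is at most M/3. Where b + X exceeds M, flag a score at or near the maximum under a separate label, because it shows a high level and does not prove worsening. Name the alert measure and its range beside the rule. The cost is about a line of wording and scoring code. The downside is more notifications, some to people who have not worsened.

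**This trial.** The Continuation section records that data collection ended in January 2019, with analysis still under way, so the alert cannot be changed for these participants. If worsening by this rule is reported among the safety results, state how many participants had a baseline that made it unattainable, and give the absolute score change by baseline band and training condition. The cost is one table from existing data.
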